### New Developments:

The in-office HIRREM approach used for research since 2011 remains very operator dependent (extensive Technologist education and experience required), and requires a lot of time for sessions (typically 10-20 sessions of 90-120 minutes each). To reduce the length of sessions, and reduce operator dependence, while increasing scalability, a new generation of hardware and software has been developed. Although based on the same core technology and algorithms for rapidly mirroring brainwaves back as audible tones in a closed-loop paradigm, the improved device includes the use of faster, 64-bit processing architecture for faster feedback, the use of 4 sensors, and the use of a standard series of protocols, all done with eyes closed (HIRREM-SOP). Although only 2 sensors are active at one time, the Technologist can apply 4 sensors at the same time. The software can switch from one pair to the other automatically, which effectively cuts in half the number of sensor placement changes needed during a session, yielding a shorter session time with fewer interruptions.

Informed by experience with prior controlled trials, the placebo condition has also been modified. The modified approach includes intentional randomness to both the pitch of the tones, as well as the timing and occurrence of the tones. In addition, characteristics of the tones themselves are not acoustically engineered. This appears to hold great promise as an improved placebo condition for use as a control in research evaluating this intervention.

This pilot study will evaluate feasibility of using this standardized, enhanced approach with HIRREM-SOP, and the effectiveness of the blinding for the placebo condition, in participants with symptoms of insomnia.

### Research Design and Method:

#### Objectives:

##### Primary Objective:

The primary objective of this randomized pilot study is to evaluate the effect of 10 sessions of standardized acoustic stimulation linked to brain activity (HIRREM-SOP, BCC), compared to 10 sessions of nonspecific acoustic stimulation not linked to brain activity (randomly generated, nonspecific tones, NCC), in addition to continued current care, on symptoms of insomnia, based on change in ISI score from V1 to V3.

##### Secondary Objectives:

The secondary objective is to evaluate the effectiveness of blinding for the placebo condition based on the expectation measure regarding group assignment prior to the 5th session.

##### Tertiary/Exploratory Objectives:

Evaluate whether the addition of acoustic stimulation linked to brainwaves (BCC group), as compared to the addition of nonspecific acoustic stimulation not linked to brainwaves (NCC group), to continued current care, will result in greater differential changes in a variety of physiological, and behavioral outcome measures outlined below.

1. Autonomic nervous system functions, as manifested by heart rate, HRV, and BRS. We expect to see greater changes in autonomic activity and an improvement of sympatho-vagal balance in the BCC group. This would be reflected as changes in heart rate, and an increase of HRV and BRS parameters such as the standard deviation of the R-R interval (SDNN), rMSSD, HF alpha, and Sequence Up, Down, or All.
2. Additional behavioral outcomes such as insomnia (assessed by the Pittsburgh Sleep Quality Index, PSQI; and the Epworth Sleepiness Score, ESS), depression (as assessed by the Center for Epidemiological Studies-Depression Scale, CES-D), anxiety (as evaluated by the GAD-7), and stress (as assessed by the Perceived Stress Scale, PSS). We expect to see greater improvement in these symptom inventory scores in the BCC group.

Overview:

This will be a single site, single blind, placebo controlled, pilot clinical trial, enrolling adults who have insomnia. Assuming a potential dropout rate of 20%, up to 24 subjects will be enrolled to achieve a target of 20 subjects (10 per group) that complete the study. Subjects aged 18 or older, with symptoms of at least mild insomnia as defined by either subthreshold, moderate, or severe clinical insomnia by the Insomnia Severity Index (ISI  $\geq 8$ ), not attributable to another known cause (e.g. obstructive sleep apnea, restless legs syndrome, benign prostatic hypertrophy), will be randomly assigned to receive 10 sessions of acoustic stimulation linked to brain activity over 4 weeks (BCC), or 10 sessions of acoustic stimulation not linked to brain activity over 4 weeks (NCC). Sessions will be 1-1.5 hours in length. Both groups will continue their other usual care throughout.

There will be pre- and post-intervention data collection to include physiological outcomes (BP, HR, and measures of autonomic cardiovascular regulation), as well as symptom inventories for insomnia (Insomnia Severity Index, ISI, Pittsburgh Sleep Quality Index (PSQI), and the Epworth Sleepiness Score (ESS), depression (Center for Epidemiological Studies- Depression Scale, CES-D), anxiety (Generalized Anxiety Disorder-7, GAD-7), and stress (Perceived Stress Scale, PSS).

Measures will be collected at an enrollment visit (V1), and the intervention will begin 0-14 days thereafter. Post-intervention data collections will be obtained at 0-14 days (V2) following completion of the intervention, and 4-6 weeks (V3, primary outcome) following V2. Analyses for primary outcomes will include differential change in ISI from V1 to V3, and the expectation measure for group assignment prior to the 5th session. The blind will be broken at the V3 visit, and those in the NCC group will be offered the opportunity to cross over to receive acoustic stimulation linked to brainwaves. All study personnel except for the Technologists will remain blinded to group assignment, so that data collection will be carried out by individuals without knowledge of group assignment.

Sample Size and Statistical Analysis:

As a pilot study evaluating upgraded technology, and a standardized protocol, there are no data on which to base formal sample size estimates. The protocol is thus written with the goal of having 20 subjects (10 per group) to be enrolled and complete the study. For analysis, we will utilize linear mixed models (LMMs) to contrast longitudinal changes in ISI scores between the BCC and NCC groups. Mean contrasts will be used to compare the changes in ISI between groups from V1 to V3, our primary test of efficacy. Comparisons of changes in all secondary outcomes will be assessed in a similar fashion.

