**Methods:**

This will be a randomized, single site, double-blinded, placebo-controlled, pilot clinical trial, enrolling adults aged 18 or older, who have self-reported symptoms of at least mild insomnia. Up to 24 will be enrolled, seeking 20 to complete the protocol. Participants will be randomly assigned to receive 10 sessions of either acoustic stimulation linked to brainwave activity (HIRREM-SOP, BCC), or nonspecific acoustic stimulation with randomly generated tones not linked to brain activity (nonspecific acoustic stimulation, NCC), using otherwise identical study procedures, over a maximum of 4 weeks. Both groups will continue their other current care throughout. There will be pre- and post-intervention data collection to include physiological outcomes (BP, HR, and measures of autonomic cardiovascular

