All baseline measures will be collected during the enrollment visit (V1), which will require 45-60 minutes. Zero to fourteen days after V1, participants will commence 10 sessions of acoustic stimulation linked to brain activity or not linked to brain activity, to be received over a one-month period. Since this is a fixed-dose intervention, every attempt will be made to complete all sessions within a two-week period. Sessions will be 1-1.5 hours in length. Participants will receive the first two sessions on consecutive days when beginning the intervention, and the first 3 sessions within the first five calendar days. To minimize participant time, following the first two sessions received as single sessions on consecutive days, up to two sessions might then be received per day, with a break of at least one hour between sessions.

Zero to fourteen days after the final intervention session there will be a post-intervention data collection visit (V2). All measures will be repeated. Four to six weeks after completion of the V2, there will be a post-intervention data collection visit (V3), with all measures repeated. Data collected at the V3 visit will comprise the primary outcome data for the study. The V2 and V3 visits are expected to require about 30 minutes. At V3, official study involvement is complete for those in the BCC group, while those randomized to the NCC group will be offered an opportunity to receive acoustic stimulation sessions linked to brainwave activity, to begin within one month of the V3 visit. Those who opt to do so will receive a course of acoustic stimulation linked to brainwaves, will continue to be followed for data collections at 0-14 days (V4) after crossover sessions, and 4-6 weeks (V5) after V4.

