In contrast, and toward the goal of evolving the paradigm for clinical trial methodology with respect to HIRREM-SOP, the present study is based on a maximally reductionistic hypothesis-testing and analysis strategy. In order to specifically identify the role of software algorithms – and to reduce not only provider-subject interactions but also limit the Technologist evaluation of brain activity patterns – as the basis for potential improvements, HIRREM-SOP sessions will be delivered based on a fixed set, and number of protocols (standard operating procedure) that will be identical for every client. The HIRREM-SOP protocols are designed based on cumulative experience of key personnel from the Wake Forest School of Medicine – Brain State Technologies academic-industry collaboration. These standardized protocols are projected to permit a robust majority of the benefits that have been reported to date, without introducing new or additional risk. Standardization of the HIRREM-SOP process will also reduce variability in the intervention delivery and thereby strengthen the generalizability of the study findings.

HIRREM-SOP sessions consist of only four potential paired placement options that are all run with eyes closed (F3/F4 and P3/P4, C3/C4 and O1/O2, FP1/FP2, and T3/T4, and AFZ/POZ and CB1/CB2). Each paired protocol will run two pairs of montages so that the participant is able to relax and have fewer disruptions during a session. In the past, the Technologists would change the placements between each protocol, so this will effectively cut in half the number of times the participant is interrupted while relaxing. While four sensors are placed on the participant's head at once, only two sensors are actively

mirroring. The other two sensors are simply observing how the brain is responding and recording that data. Each pair of protocol is set to play one at a time. For example, in the pair F3/F4 and P3/P4, F3/F4 will be mirrored back while P3/P4 are only observed. When the F3/F4 exercise concludes, the program will automatically start the P3/P4 mirroring protocol, while F3/F4 will be observed. At each location, based on the electrical pattern at the time, HIRREM-SOP software chooses what protocol will best support that area to relax itself. This process also provides information on how the brain is responding globally to shifts occurring locally.

Non-specific acoustic stimulation:

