Individuals assigned to the nonspecific acoustic stimulation group (NCC) will undergo sessions that mimic HIRREM-SOP in all appearances and procedures, including behaviors and subjective intentionality of the Technologist, and the number and scalp locations of protocols delivered during each session. However, in place of acoustic stimulation consisting of tones that vary in pitch and timing based on algorithmic analysis of real time brain activity, participants assigned to the NCC group will receive tones generated by a random signal generator. This includes randomness for both the timing, and the pitch of the tones, which are also not acoustically engineered. Technologists will be specifically instructed and trained to maintain comparable mental and behavioral interactional styles with all participants, both to minimize or eliminate confounding effects of Technologist subjectivity on differential outcomes associated with BCC and NCC groups, and to maintain subject blinding.

Safety:

Based on experience reported by Brain State Technologies, garnered from provision of case management support, feedback from their clients, and feedback from the HIRREM provider community, as well as results from IRB-approved studies at WFSM (now about 500 participants who have received HIRREM), the study team is not aware of any serious adverse events resulting from HIRREM sessions.

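### Do two conflicting blinding labels, and unblinding at the primary-outcome visit, leave it unclear how this trial is blinded?

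*Combined protocol and SAP*

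**What the plan says.** **Labels.** The Methods section of the Abstract says "This will be a randomized, single site, double-blinded, placebo-controlled, pilot clinical trial". The Overview, in Research Design and Method, says "This will be a single site, single blind, placebo controlled, pilot clinical trial".

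**Roles.** The Overview states that "All study personnel except for the Technologists will remain blinded to group assignment" and gives the purpose: data are to be collected by people who do not know the group. The section on non-specific acoustic stimulation trains Technologists to behave alike with everyone, partly to limit their influence on outcomes "and to maintain subject blinding".

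**Unblinding.** The Overview says "The blind will be broken at the V3 visit, and those in the NCC group will be offered the opportunity to cross over". Under Number of Sessions and Length of Study, V3 is described thus: "there will be a post-intervention data collection visit (V3), with all measures repeated". That section names the V3 data as the primary outcome data. The Expectation Measure section has participants guess their group at V1, before the fifth session and at V3.

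**The concern.** The labels cannot both be right if each carries its usual meaning. A reader of the Abstract alone could assume that those delivering the sessions do not know the allocation. A reader of the Overview's first sentence alone could assume that the data collectors do know it. The effectiveness of blinding is this trial's only secondary objective, so a muddled description is awkward.

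The timing looks more serious at first sight. The ISI is a seven-item questionnaire that the participant completes, scored 0 to 28. Blinded data collectors do not protect a self-report from a participant who has just learned the allocation. If disclosure came first at V3, control participants told that they had received random tones, and active participants told that they had received the real intervention, might answer differently. With about 10 completers per group, that would bear directly on the V1-to-V3 contrast. The V3 group guess would also be worthless.

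**Working it through.** No sample size, power or error-rate figure depends on this point, so the check is a comparison of the text.

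**1. Is there a conflict of procedure behind the labels?**

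| Role | Knows allocation before V3? | Source |
|---|---|---|
| Participant | No | Non-specific acoustic stimulation; Expectation Measure |
| Data collectors and other personnel | No | Overview |
| Technologists | Yes | Overview |

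No section contradicts any row. Some would call this arrangement single blind because those delivering the intervention are unblinded. Others would call it double blind because participants and assessors are blinded. The roles are the same under either name.

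**2. Is the influence of the unblinded Technologists addressed?** Yes. On the active arm, "HIRREM-SOP sessions will be delivered based on a fixed set, and number of protocols (standard operating procedure) that will be identical for every client", which limits discretion. Control participants "will undergo sessions that mimic HIRREM-SOP in all appearances and procedures", and the Technologists are trained to keep their interaction comparable.

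**3. What order does the text imply at V3?**

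- The Expectation Measure section asks for a guess of group at V3. That question is meaningful only before disclosure.
- The Overview requires data collection by people without knowledge of the group, and the sentence doing so directly follows the one on breaking the blind.
- Number of Sessions and Length of Study describes the repetition of all measures first, then identifies these as the primary data, and only then mentions the crossover offer.
- The Abstract places the crossover offer after V3.
- Other Data Collection, Measures, and Process places crossover after the participant's initial commitment is finished.

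All five point to measures first. No sentence points the other way.

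**4. What could be affected at all?** The blinding outcome uses the guess before the fifth of 10 sessions. V2 falls 0 to 14 days after the last session, and V3 falls 4 to 6 weeks after V2. That guess therefore precedes V3 by at least 0 days + 4 weeks = 4 weeks, whatever happens within V3. Only the V3 measures could be touched, and under measures-first they are not.

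**The case for a change.** The best case for a change is that a site should not have to assemble a visit procedure from several sections. The wording of the offer does vary: after V3 in the Abstract, at V3 under Number of Sessions and Length of Study, and in the same sentence as unblinding in the Overview. A guess made before disclosure also does not strictly prove that the ISI came before it. A misreading could recur at every V3 visit, and the contrast would then shift by the difference between the two arms' average reactions to disclosure. The documents give no figure for that, so it cannot be bounded here.

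Part of this stands. The labels do differ, and no readable sentence gives the order outright. However, the argument needs staff to take an order that no section suggests and that would defeat the V3 guess they are told to collect. The study flow chart, another figure near the account of sessions and visits, and the contents of Appendices B and C were not available in the text examined. Any of them may already show the order, so its absence from the readable text is not evidence of absence from the plan.

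**Conclusion.** No change to the plan follows. The two labels are a clerical inconsistency: the roles are stated and consistent, and settling on one label would alter no procedure, analysis or result. If the text is revised for other reasons, describing the blinding by role in both places would be a reasonable editorial tidy-up, and so would a line or cross-reference on the V3 order.

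The V3 order is a detail that staff and analysts would fill correctly from what is written. On that reading the effect on the primary ISI contrast is zero. The secondary blinding outcome is unaffected on any reading.

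This conclusion rests on two assumptions: that V3 is run in the order the text implies, and that the unseen flow chart and appendices do not contradict it.

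### Minor: at the assumed 20% dropout, 24 enrolled gives 19.2 expected completers, just under the target of 20; 20 of 24 implies 16.7% dropout

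*Combined protocol and SAP*

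**What the plan says.** The figures appear in three places in the combined protocol and SAP.

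- **Overview (Research Design and Method):** "Assuming a potential dropout rate of 20%, up to 24 subjects will be enrolled to achieve a target of 20 subjects (10 per group"). This is the only place that gives a dropout rate.
- **Methods (abstract):** "Up to 24 will be enrolled, seeking 20 to complete the protocol". The same ceiling and the same number sought, with no dropout rate.
- **Sample Size and Statistical Analysis:** "The protocol is thus written with the goal of having 20 subjects (10 per group) to be enrolled and complete the study". The same goal, again with no dropout rate. This section also says that "there are no data on which to base formal sample size estimates".

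No section shows how 24 was obtained, gives a different dropout rate, or allows enrolment above 24.

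**The concern.** The Overview sentence presents 24 as the enrolment that yields 20 completers under 20% dropout. Any two of those figures fix the third, and the three given do not fit together. Because 24 is a ceiling, enrolling fewer only widens the gap.

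Little is at stake for this trial's inference, since nothing quantitative rests on the 20. Two practical points remain. First, the Importance section of the abstract says the pilot is meant to confirm feasibility and to help plan later controlled trials. Retention is a natural part of feasibility, and a reader comparing observed dropout with the plan cannot tell whether the allowance was 20% or about 17%. Second, if the allowance was added to the target, the same method in a larger trial would again deliver only 1.20 × 0.80 = 96% of the target at 20% dropout, which is a larger absolute shortfall.

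**Working it through.** **Inputs**

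- Dropout rate d = 20% (Overview)
- Maximum enrolment N = 24 (Overview; abstract Methods)
- Target completers n = 20, 10 per group (Overview; Sample Size and Statistical Analysis)

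**1. Reproducing the plan's figure.** Adding the allowance to the target, n × (1 + d) = 20 × 1.20 = 24, matches exactly. This is an inference about how 24 arose, since no formula is given.

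**2. Expected completers at the stated ceiling.** N × (1 − d) = 24 × 0.80 = 19.2, or 9.6 per arm if the arms are equal. Shortfall: 20 − 19.2 = 0.8.

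**3. Dropout rate implied by 24 and 20.** 1 − 20/24 = 4/24 = 16.7%.

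**4. Enrolment needed for 20 expected completers at 20% dropout.** n/(1 − d) = 20/0.80 = 25. With equal arms, 10/0.80 = 12.5 per arm, rounded up to 13, so 26 in total (13 × 0.80 = 10.4 expected completers per arm).

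**5. Chance of reaching the target.** This assumes that each participant drops out independently with probability 20%, which the protocol does not state.

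| Enrolled | Expected completers | P(at least 20 complete) |
|---|---|---|
| 24 | 19.2 | 46% |
| 25 | 20.0 | 62% |
| 26 | 20.8 | 75% |

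With 12 per arm, each arm reaches 10 with probability 0.558, so both do with probability 0.558² = 31%.

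**6. Illustration of the effect on precision.** For a simple two-group comparison of completers, the 95% CI half-width in SD units is t(0.975, df) × √(1/n₁ + 1/n₂):

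- 10 and 10: 2.1009 × 0.4472 = 0.940
- 9 and 10: 2.1098 × 0.4595 = 0.969

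The standard error rises by 0.4595/0.4472 − 1 = 2.7%, and the interval widens by 0.969/0.940 − 1, about 3%. This shows one plausible outcome (19 completers) and is not a bound. The planned analysis is a linear mixed model over visits, which can use V1 and V2 data from someone who misses V3, so these percentages only indicate scale.

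**The case against.** The strongest reply is that the discrepancy is immaterial. It is less than one expected completer, and 24 follows from a common shorthand of adding 20% to the target. The sentence also uses planning language: the dropout rate is a possibility, 24 is an upper limit, and 20 is a target rather than a forecast. The target can still be reached, with a 46% chance under independent 20% dropout. No power, precision target or decision rule uses the 20. The figure of 26 depends on equal allocation, which is inferred from 10 completers per group because no allocation ratio is stated.

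Most of this stands, and it sets the severity. It does not make the figures consistent. The sentence assumes the 20% rate and offers 24 as the enrolment that achieves 20, so the three numbers are tied together. The shorthand explains where 24 came from, but 20% is lost from those enrolled, not from the target. Reading 24 as an upper limit does not help either, because the shortfall exists at the limit itself.

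**Conclusion.** The concern holds, at the lowest level of severity. The Overview's dropout assumption does not deliver its completer target at its enrolment ceiling: 19.2 expected against 20, a gap of 0.8 of a completer. Put as enrolment, 24 is one short of the 25 needed, or two short of 26 if arms are equal. Put as dropout, 24 and 20 together imply 16.7%, not 20%.

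These results are plain arithmetic on the protocol's own numbers. Only the figure of 26 (equal arms), the probabilities (independent dropout) and the precision illustration (two-group comparison of completers) rest on added assumptions. No stated power, effect size or conclusion changes. The abstract and the sample size section repeat 24 or 20 without a dropout rate, so they are not separate errors.

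**What to change.** Keep the ceiling at 24 and restate the Overview sentence in one of two ways:

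1. Keep the 20% dropout rate and say that enrolling 24 would be expected to yield about 19 completers, noting that this is just under the goal of 20 given in the abstract and the sample size section.
2. Keep the target of 20 and say that a ceiling of 24 allows for about 17% dropout (4 of 24), making clear that this rate is only what the ceiling and target imply and is not supported by data.

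Either is a one-line text correction with no extra participants and no change to procedures or analysis. The first concedes an expected number slightly below the goal; the second states a smaller dropout allowance than the 20% now assumed. Raising the ceiling to 25 (26 with equal arms) would preserve both the 20% and the 20, but it adds participants and is not needed because no stated power depends on the number.

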Since 2011, the HIRREM Research Program at WFSM has enrolled almost 500 participants in six IRB-approved clinical studies to evaluate the effects and potential benefits of HIRREM. Use of HIRREM has been associated with reduced sleep symptomatology and reduced high frequency amplitudes in adults with insomnia [23], reduced menopausal symptoms in women [24], improved sleep in athletes with persisting post-concussion symptoms [25], reduced symptoms, and temporal lobe high frequency asymmetry in self-reported post-traumatic stress [26], and reduced symptoms of military-related traumatic stress [26]. Improved autonomic cardiovascular regulation has also been observed in those receiving HIRREM, including a cohort of adolescents with Postural Orthostatic Tachycardia Syndrome [27]. In addition, correlation has been reported between high frequency electrical brain pattern asymmetry scores at baseline, and measures of autonomic cardiovascular regulation [28].

In addition, a placebo controlled efficacy trial of in-office HIRREM for moderate to severe insomnia demonstrated a clinically meaningful reduction of insomnia symptoms ( $\geq 7$  point reduction on the ISI), and statistically significant additional benefit associated with use of HIRREM, as compared to a sham placebo of random audible tones not linked to brainwaves [29]. HIRREM was well tolerated, and the benefit was durable through the final follow up visit, 4 months after completion of the intervention (Figure 1).

Continuous recording (10 minutes) of blood pressure and heart rate also allowed for analysis of autonomic cardiovascular regulation, including multiple measures of heart rate variability and baroreflex sensitivity. Data were obtained at all study visits. Analysis demonstrated significant improvement in multiple objective measures of autonomic cardiovascular regulation including increased baroreflex sensitivity (HF $\alpha$ , and Sequence ALL) and heart rate variability (SDNN, and rMSSD), associated with this short term use of in-office HIRREM, compared to a placebo intervention of random audible tones not linked to brainwaves (Figure 2). The benefit was seen at all follow up data collections, and was durable through the final follow up at 4 months post-intervention [30]. There was no significant improvement seen in the placebo group at any time point. It is not clear whether these results reflect a cause, an effect, or both relative to the observed improvement of insomnia symptoms.

Figure 1:

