#### Participants/Subjects:

Adults ages 18 and older who have self-reported insomnia, who also meet inclusion criteria outlined below, and who are interested in receiving acoustic stimulation linked to brainwaves or acoustic stimulation not linked to brainwaves, will be considered for possible enrollment. Subjects will be recruited by physician referral, word of mouth, and through advertisement. The participant must be able to provide informed consent.

Interested subjects will be informed with a more detailed description of the study, and the extent of the time commitment will be explained through phone calls or email communications. If no exclusions are apparent from initial phone or email communications, potential participants will complete an online eligibility screening form, which will be reviewed by the study team.

As part of the informed consent process, study procedures, schedule for visits, and duration of participation will again be reviewed, and alternatives discussed, including the option to not enroll in this project, and follow up with their primary health care provider. For those confirmed to have an eligible baseline ISI score, baseline study measures obtained, and randomization will be completed prior to the start of the intervention. Those scheduled for an enrollment visit will also be provided a copy of Appendix B, Handout to Study Participants, and a welcome email with details.

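### No blocking or stratification is stated and the primary ISI change contrast has no severity term, although entry runs from ISI 8 upward and V1 ISI is known before randomisation

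*Combined protocol and SAP*

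**What the plan says.** The abstract's Methods describe allocation only as follows: "Participants will be randomly assigned to receive 10 sessions of either acoustic stimulation linked to brainwave activity", or to the nonspecific tones. Under Participants/Subjects, once an eligible baseline ISI is confirmed, "randomization will be completed prior to the start of the intervention". No section states blocks, strata, how the sequence is generated or how it is concealed. A 1:1 ratio is implied by the target of ten per group, which the Overview gives as "up to 24 subjects will be enrolled to achieve a target of 20 subjects (10 per group) that complete the study". Sample Size and Statistical Analysis repeats it: "The protocol is thus written with the goal of having 20 subjects (10 per group) to be enrolled and complete the study".

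Entry covers "symptoms of at least mild insomnia as defined by either subthreshold, moderate, or severe clinical insomnia by the Insomnia Severity Index" at a score of 8 or more. The earlier controlled study in the Background was "a placebo controlled efficacy trial of in-office HIRREM for moderate to severe insomnia", so this trial admits a milder group than that one did.

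For the primary test, Sample Size and Statistical Analysis plans linear mixed models with a mean contrast of V1-to-V3 ISI change between groups. It names no severity stratum and no baseline ISI covariate.

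**The concern.** How far ISI can fall depends on where it starts. Someone entering at 8 can fall by 8 points at most; someone entering at 24 has three times the room. Higher entry scores are also more exposed to regression to the mean. With about ten completers per arm, chance can put noticeably more of the milder cases in one arm. Subtracting V1 removes the difference in level but not the dependence of change on level, so part of the observed contrast would reflect who landed where.

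This matters because the Importance section says the trial is to supply effect-size estimates for planning later controlled trials. The balancing variable is already in hand when assignment is made, and the plan uses it neither in allocation nor in analysis.

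**Working it through.** **The plan's own figure.** 20 completers x 1.2 = 24, which reproduces the enrolment figure. Dividing by the retained fraction gives 20/0.8 = 25, a minor gap. Expected completers from 24 are 24 x 0.8 = 19.2.

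**Assumptions, because the documents give no severity mix.** Subthreshold is taken as ISI 8-14, evenly spread (mean 11, variance 4). The rest is taken as 15-24, evenly spread (mean 19.5, variance 8.25). The subthreshold share p is about one half, then varied.

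**Baseline difference, unstratified, 10 per arm.** The variance of V1 ISI at p = 0.5 is (4 + 8.25)/2 + 0.25 x 8.5² = 6.125 + 18.06 = 24.19. The SD of the difference in arm means is sqrt(24.19 x 2/10) = 2.20. Arm means move in steps of 0.1, so a gap of 2 or more is cut at 1.95: P = 2 x [1 - Φ(1.95/2.20)] = 38%.

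Other shares:
- p = 0.25: variance 1 + 6.19 + 13.55 = 20.73, SD 2.04, P about 34%.
- p = 2/3: variance 2.67 + 2.75 + 16.06 = 21.47, SD 2.07, P about 35%.

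**With stratification.** Perfect balance within bands and no dropout leaves only the within-band variance: sqrt(6.125 x 0.2) = 1.11, and P is about 8%. That is a limit, not what a real list delivers. Simulating 24 participants with blocks of 2 and 4 in two bands and 20% dropout gives about 20%, because blocks are left incomplete and dropout undoes some of the balance.

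**Counts of subthreshold cases.** Chance that the two arms differ by 4 or more (binomial for simple assignment, hypergeometric for a fixed 12:12 split without strata):

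| Subthreshold among 24 | Simple | Fixed 12:12, no strata |
|---|---|---|
| 6 | 22% | 15% |
| 8 | 29% | 19% |
| 12 | 39% | 22% |
| 16 | 45% | 19% |

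Fixing the arm sizes therefore does not by itself balance severity.

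**Effect on the contrast.** Suppose ISI falls by 45% of V1 on active and 20% on placebo (assumed). At a common mean of 15.25 the contrast is 0.25 x 15.25 = 3.8. A gap of D in mean V1 ISI shifts it by (0.45 + 0.20)/2 x D = 0.325D, so D = 2 shifts it by 0.65 points. A 30-point gap in subthreshold share gives D = 0.3 x 8.5 = 2.55 and a shift of 0.83, to about 3.0 or 4.6. If exactly 10 of 20 completers are subthreshold, a gap that large occurs in 18% of 10:10 trials. It occurs in 26% if the number of subthreshold cases also varies at random. With a purely additive effect, no floor and no regression to the mean, the shift is zero.

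**Overall gain.** Take 9.6 completers per arm and a residual SD of change of 4 (assumed). The SD of the contrast is sqrt[(0.45² + 0.20²) x 24.19/9.6 + 2 x 16/9.6] = sqrt(0.61 + 3.33) = 1.99. With the between-band part removed it is sqrt(0.15 + 3.33) = 1.87, or 6% less. With a residual SD of 6 the figures are 2.85 and 2.77, or 3% less. Simulation with uneven arms and dropout gave about 2.03 falling to 1.88-1.90, or 6-7% less.

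**The case against.** The strongest reply is that silence on method is not a faulty method. No section says assignment is simple, blocking may be intended, and the study flow chart cannot be read in the text available. A reader might infer that allocation is unrestricted; the documents do not support that. They support only that the method is not described, so every figure above is conditional on no stratification.

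A reader might also infer that the allocation fails to deliver ten per group. The plan calls this a target and a goal. Under simple assignment 24 people give at least ten per arm at entry 69% of the time. With 20% dropout both arms reach ten completers in 14% of trials, but a fixed 12:12 split reaches it in only 31%, and stratified small blocks in about 29%. Dropout is the main cause, and blocking does not secure the target.

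Nor do unequal arms cost much precision: sqrt(1/7 + 1/13)/sqrt(2/10) = 1.05, a 5% larger standard error at 7:13. The 7-point reduction in the Background is a result of the earlier trial, not a criterion in this one.

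It is also fair to say that chance imbalance is not bias, and that a confidence interval already reflects it. That stands: the gain is in precision and in how well a single small estimate can be read.

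Finally, adjustment for V1 ISI alone would meet much of the concern without strata, and a mixed model that constrains both arms to a common V1 mean would do so in effect. The plan states neither.

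**Conclusion.** The point holds as an unstated and improvable design choice. The plan states no blocking or stratification and no severity term, while admitting a wide ISI range and holding V1 ISI before assignment. If allocation is unstratified, a V1 gap of 2 points or more arises in about 38% of trials at a half subthreshold share (34-35% at a quarter or two thirds), against about 20% with stratified small blocks and 20% dropout. The effect on the contrast runs from nothing (additive response) to about 0.65 points per 2-point gap (the assumed proportional response). The overall gain in the SD of the contrast is about 3-7%. The severity mix, response rates and residual spread are all assumptions. The finding does not extend to a claim that randomisation is simple, that ten per group is lost through it, or that unequal arms are costly.

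**What to change.** In the abstract's Methods and in the Overview, state: 1:1 allocation by permuted blocks of randomly varied, undisclosed size, stratified by V1 ISI band (subthreshold versus moderate or severe, with the cut-point written down), from a list prepared in advance and held by someone who does not enrol participants.

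In Sample Size and Statistical Analysis, adjust the V1-to-V3 change contrast for V1 ISI. Use it as a covariate in a model for change, or include a band-by-visit term in the mixed model. A band main effect alone shifts level at every visit and does not adjust change.

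The cost is one prepared list, one extra entry at randomisation and one model term; no visit, measure or participant is added. The downside is predictability. The plan leaves the Technologists unblinded throughout at a single site, so they see each assignment as it is delivered, and blocks of 2 within two small strata are partly guessable. Varied block sizes and a list kept away from enrolling staff limit this but do not remove it. If the sponsor judges that risk too high, adjustment for V1 ISI should still be kept.
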